1.3 Research questions

The present study aims to respond the following research questions (RQ).

- 1. Is there any difference between the game performance of older adults with typical cognition and individuals with MCI?
- 2. What is the concurrent validity of the game-based screening for MCI detection?
 - 2.1 Is there any relationship between game performance and total score of traditional cognitive tests (MoCA score and Quick MCI (Qmci)) in older adults with typical cognitive and older adults with MCI?
 - 2.2 Is there any relationship between the sub-MoCA scores and sub-Qmci scores and the game metrics in older adults with typical cognitive and older adults with MCI?

- 3. What is the diagnostic accuracy of the game-based screening assessed by sensitivity, specificity, accuracy, and the Area Under Curve (AUC) of the game-based screening for MCI detection?
- 4. Is game performance an associated factor with cognitive status controlled by demographic variables?
- 5. Is there any difference between the level of state anxiety while playing the G3 game and while administering traditional cognitive tests in older adults with typical cognition and individuals with MCI?
- 6. What is the usability of the G3 as a game-based screening?

2. Literature review

This chapter will address several key areas essential for understanding the use of SCGs in cognitive screening for MCI. It will begin with an overview of cognitive functions and their domains, followed by a discussion of MCI, its prevalence, and associated brain changes. The review will then examine cognitive changes with aging and MCI, traditional cognitive tests used for MCI diagnosis, and their limitations. It will explore digital technologies for MCI screening, focusing on the potential of SCGs. Finally, the chapter will highlight research gaps and propose directions future studies, emphasizing the investigation of the G3, a SCG designed for older adults, for MCI detection.

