2.3.5 Serious Computer Games as screening tools for MCI

Only a handful of studies have applied SCGs for MCI screening, revealing significant differences in game performance between older adults with MCI and their healthy counterparts For instance, Zygouris et al. noted that individuals with MCI took significantly longer to complete games than their healthy counterparts (t = 4.84, p < 0.001) (139). Similarly, Gielis et al. observed distinct differences in 12 out of 23 digital biomarkers, including time-based, errorbased, and result-based metrics, highlighting substantial discrepancies between the two groups (140). Therefore, the SCGs could differentiate or classify older adults with and without MCI. However, more studies are needed to test more game scenarios and investigate the association of demographic factors with game performance in PwMCI and healthy counterparts. Research has also explored the criterion validity of the game-based screenings for MCI detection, highlighting significant correlations between game metrics and cognitive status (39,41,139–146). Numerous game metrics, including completion ability, gameplay duration, accuracy of actions, and total score, have been examined for their relationship with cognitive status. For instance, Zygouris et al. found a negative correlation (r= -0.2) between game playtime and cognitive test scores, suggesting that older adults with lower cognitive status required more time to complete games (139). Zygouris et al. also found correlations between education (r= -0.3 and r = -0.23) and age (r = 0.2 and r = 0.24) with the total time needed to complete the game (22,139). It means that a higher education level is associated with faster game completion, while older age correlates with longer completion times. Cabinio et al. found a correlation between game performance accuracy, reaction time, total playing score and cognitive status in PwMCI and the comparison group (43). Although these findings affirm the criterion validity of gamebased screenings, the correlations are not strong. Only one study explored the correlation of the

demographic variables and the game performance. Further research is necessary to clarify the relationships between traditional cognitive screening scores and various game metrics, evaluating the validity of game-based screenings.

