3.6 Variables

The study variables are the following:

- Game performance collected through various game metrics, including total time of
 playing, the ability to complete the whole game, the ability to manage the budget, number
 of errors, the number of checking the shopping list, and the game performance accuracy.
 - Total Time of playing: This numerical variable refers to the total time that takes to complete all 6 stages in seconds with the maximum of 1800 seconds.
 - The ability to complete the game: This binary variable (1= Could complete, 0= Could not complete) refers to the participant's ability to complete all the 6 stages of the game.
 - The ability to manage the budget: This binary variable (1 = Could manage, 0 =
 Could not manage) refers to the participant's ability to keep their purchases equal to or below the budget limit provided for each level.
 - The number of errors: This numerical variable refers to the total number of mistakes made by participants, including mistaken, missed, and repeated items purchased.
 - The number of times the participant opens up the reading list: This numerical variable refers to the total number of times the participant open and check the shopping list within the 6 stages.
 - O The game accuracy: This numerical variable represents the success in the game, ranging from 0 to 100, where higher values mean higher game performance.

Demographics

 Age (In number of years): It refers to the chronological age of an individual in years at the time of data collection. This variable is considered as numerical in this study.

- Sex at birth: It refers to sex assigned at birth. Categories for this variable are male and female.
- Level of education: It refers to the highest degree or level of school completed by the participants. Categories for this variable are elementary school, high school, bachelor's degree, master's degree, and higher.
- Technology savvy: This categorical refers to the familiarity and experience of the
 participants with technology. It will be collected and measured based on the
 number of technological devices they use and the frequency of their usage.
- Living status: It refers to the participants' living condition. Categories for this
 variable are living alone, living with family, and living in an institution

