3.9 Data analysis

To explore the difference between game performance in PwMCI and healthy comparison group (RQ1), the Unpaired t-test or Mann-Whitney U test as appropriate (155), with an α level of 0.05, will be applied. If the mean difference is statistically significant, it indicates that G3 can classified older adults with typical cognition and older adults with MCI based on their game performance. In addition, a two-way factorial multiple analysis of covariance (MANCOVA) (155) will be performed to compare the effects of demographics as covariates on the differences between groups.

To explore the association between the game performance and traditional cognitive tests, including MoCA and Qmci (RQ2), correlational analysis (155) between the game metrics and the scores of each traditional cognitive tests, including total score sub-scores such as memory and executive functions will be conducted. If the correlation coefficient (r) is positive closer to one, it means that the concurrent validity of G3 as an MCI screening tool is good.

To investigate the diagnostic accuracy of the game-based screening (RQ3), formulas will be used as follows:

Sensitivity: Proportion of true positives correctly identified = $\frac{TP}{TP+FN}$

Specificity: Proportion of true negatives correctly identified = $\frac{TN}{TN+FP}$

Accuracy: Overall correctness of the testx = $\frac{\text{TP+TN}}{\text{Total Population}}$

Where TP: True Positives, TN: True Negatives, FN: False Negatives, FP: False Positives (155). Additionally, the interpretation of the Receiver Operating Characteristic (ROC) and Area Under the Curve (AUC) will be used for examination of diagnostic accuracy (155). The ROC curve is a graphical plot that illustrates the diagnostic ability of a binary classifier system as its discrimination threshold is varied. The curve is created by plotting the True Positive Rate (TPR) against the False Positive Rate (FPR) at various threshold settings (155).

The following steps will be used to calculate the ROC curve:

Firstly, the True Positive Rate (TPR), also known as sensitivity or recall, will be determined using the formula:

$$TPR = \frac{TP}{TP + FN}$$

Secondly, the False Positive Rate (FPR), also known as (1 - specificity), will be determined using the formula:

$$FPR = \frac{FP}{FP+TN}$$

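### Two interpretation rules in section 3.9 are wrong as written: a positive correlation is not the sign of validity for play time and errors (RQ2), and a significant group difference does not show that G3 can classify (RQ1)

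*Protocol*

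**What the plan says.** **RQ2.** Protocol section 3.9 plans correlations "between the game metrics and the scores of each traditional cognitive tests", covering total scores and sub-scores. It then gives a single criterion, not qualified by metric: "If the correlation coefficient (r) is positive closer to one, it means that the concurrent validity of G3 as an MCI screening tool" is good. Section 3.6 lists six game metrics: total time, completion, budget management, number of errors, number of shopping-list checks, and accuracy. Time is the "total time that takes to complete all 6 stages in seconds with the maximum of 1800 seconds". No metric is said to be reverse-scored.

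**RQ1.** Section 1.3 asks: "Is there any difference between the game performance of older adults with typical cognition and individuals with MCI"? Section 3.9 answers with an unpaired t-test or Mann-Whitney test at α = 0.05 and adds: "If the mean difference is statistically significant, it indicates that G3 can classified older adults with typical cognition and older adults with MCI".

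**RQ3.** Later in section 3.9, sensitivity, specificity, accuracy, the ROC curve and the AUC are planned. The ROC and AUC "will be used for examination of diagnostic accuracy", with a verbal scale on which 0.5 means no discrimination and the acceptable band starts at 0.7.

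**The concern.** Both sentences are stated rules for reading a result, not details left for later.

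For RQ2, validity testing is named in section 3.3 as a primary objective, and the study is sized on correlational analysis so that concurrent validity can be assessed. The sentence on the sign of r is the only criterion given for it. Followed literally, it would mark down a time or error metric that tracks cognition well, and would approve one on which people with better cognition are slower or make more errors.

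For RQ1, the planned test shows only that the groups differ on average. Classification depends on how far the two distributions overlap, which is what RQ3 measures. The sentence would let the report say that G3 can classify while RQ3, on the same metric, gives an AUC below the protocol's own acceptable band.

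**Working it through.** The plan gives no figure of its own to reproduce on this point. The first check compares passages; the second is arithmetic.

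**1. Expected sign for each metric (RQ2)**

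Direction of the tests (section 2.2.5): MoCA cut-offs are 26 for MCI and 18 for dementia, and Qmci below 62 indicates MCI. Higher scores therefore mean better cognition on both.

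| Metric (section 3.6) | Higher value means | Sign of r expected if valid | Rule in 3.9 |
|---|---|---|---|
| Accuracy, 0–100 | better | positive | right |
| Completion, 1 = yes | better | positive | right |
| Budget managed, 1 = yes | better | positive | right |
| Total time, seconds | worse | negative | wrong |
| Number of errors | worse | negative | wrong |
| Number of list checks | not fixed by the text | not fixed | cannot be judged |

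A time or error metric that tracked MoCA perfectly would give r = −1, which the rule does not call good. The protocol's own literature review goes the other way from its rule: in section 2.3.5 an earlier study "found a negative correlation (r= -0.2) between game playtime and cognitive test scores", and, with other results of the kind, "these findings affirm the criterion validity" of game-based screening.

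**2. What a significant difference implies for classification (RQ1)**

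Inputs: 29 per group (section 3.3) and α = 0.05 (section 3.9). Assumptions: two-sided test, normal scores with equal variance, and the same continuous metric in RQ1 and RQ3. The calculation does not apply to the two binary metrics.

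- Smallest significant standardised difference: d = t(0.975, 56) × √(2/29) = 0.526.
- Corresponding AUC: Φ(d/√2) = 0.645.
- Sensitivity and specificity at the midpoint cut-off: Φ(d/2) = 0.604 each.
- Mann-Whitney boundary: 0.5 + 1.96 × √(841 × 59/12)/841 = 0.650, where 841 = 29 × 29.
- Other group sizes, t-test: 25 per group gives d = 0.569 and AUC 0.656; 30 per group gives d = 0.517 and AUC 0.643.

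Working back from the start of the acceptable band, AUC 0.70:

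- d = √2 × Φ⁻¹(0.70) = 0.742, so t = 0.742 × √(29/2) = 2.82 and p = 0.0066.
- Mann-Whitney: z = 0.20 × 841/√(841 × 59/12), p = 0.0089.

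Any p-value between about 0.007 (t-test) or 0.009 (Mann-Whitney) and 0.05 therefore goes with an AUC below 0.70.

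How often this would happen depends on the true difference, which the protocol does not give. A simulation of 40,000 trials for each of three assumed values, at 29 per group, gave:

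| Assumed true d | P(t-test p < 0.05) | P(p < 0.05 and observed AUC < 0.70) | Share of significant results with AUC < 0.70 | Same share, Mann-Whitney |
|---|---|---|---|---|
| 0.5 | 0.463 | 0.262 | 57% | 55% |
| 0.8 | 0.849 | 0.254 | 30% | 28% |
| 1.0 | 0.963 | 0.126 | 13% | 12% |

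**The case against.** On RQ2, the paragraph in section 3.9 opens by speaking of game performance in general. If performance is taken as higher-is-better, a positive r is the right reading, so the sentence may be shorthand. Section 2.3.5 shows that the investigator knows longer play goes with lower cognition. The rule has no numeric threshold, and its sign changes neither the estimate of r nor the sample size. This makes an actual misreading less likely. It does not correct the rule, whose stated scope is the game metrics, with time and errors among them and no recoding.

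On RQ1, the wording is loose, RQ3 already measures classification, and the accuracy conclusion does not rest on RQ1. The AUC scale gives labels, none of them between 0.5 and 0.7, and sets no pass mark, so a just-significant result breaks no stated criterion. The simulated shares depend on assumed values of d and run from 57% down to 13%. All of this stands and limits the harm. It does not make the inference from a significant difference to ability to classify a valid one, and the boundary AUC of 0.645 does not depend on any assumed true effect.

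It is also fair to say that correcting time and errors alone leaves the list-check metric without an expected direction.

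**Conclusion.** Both sentences are wrong as written and should be corrected.

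The RQ2 rule has the opposite sign to the one expected for two of the six metrics. It is right for accuracy, completion and budget management, and cannot be judged for list checks. This follows from the protocol's own definitions.

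The RQ1 rule claims more than its test can show. At 29 per group, significance is compatible with an AUC as low as about 0.65 and with about 60% sensitivity and specificity, given a two-sided test and, for the t-test figures, equal-variance normal data. The comparison with RQ3 also supposes that the same continuous metric is used in both.

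The consequence is limited to what may be concluded. No test, estimate, sample size or RQ3 accuracy result is affected.

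**What to change.** Change two sentences in section 3.9.

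- **RQ2:** state that a negative r is expected for total time and number of errors, or reverse-score these two before analysis, and judge the size of r in the expected direction. Keep the positive sign for accuracy, completion and budget management. For list checks, either state an expected direction with a reason, or say that none is assumed and report r without a directional reading.
- **RQ1:** limit the conclusion to a difference in game performance between the groups. Rest any statement about classification on the AUC, sensitivity and specificity already planned under RQ3.

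This needs no new data, participants or analyses. The only cost is that RQ1 then supports a weaker conclusion. The expected signs should be fixed before results are seen.

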3.3 Sample size

The correlational analysis was selected for determining the sample size of this study. The main reason for that is that the diagnostic accuracy and validity testing are the primary objectives of this project. Calculating the sample size based on correlational analysis offers a robust approach

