to examining the relationship between game performance and cognitive status, requiring a moderate number of participants. Thus, this study, designed with a statistical power of 0.8, an alpha level of 0.05, and a medium effect size of 0.7, requires a minimum sample size of 58 participants. Twenty-nine older adults (65 and above) who meet the diagnostic criteria for MCI, and 29 older adults with typical cognition will be eligible to participate in the study. Other reasons for justifying the sample size include: 1) The statistical analyses to answer questions that aim to compare two conditions, or two groups requires a smaller sample size; and this small sample size is insufficient to justify correlational analysis. 2) the "Events Per Variable" (EPV) rule is often used in statistical modeling, particularly in logistic regression, to determine the minimum sample size needed to ensure reliable and valid results. The general rule is to have at least 10 events (outcomes of interest) for each predictor variable (151). Therefore, using regression analysis to explore the six associated factors (game performance, age, sex, educational level, tech savviness, and living status) with the presence of MCI would necessitate 60 events (instances of the outcome of interest). Assuming an equal distribution of events and non-events, at least 120 participants would be needed in total to achieve 60 events, ensuring that each predictor variable is adequately supported by the data and enhancing the reliability of the statistical model. However, for a feasibility study involving a brand-new, untested test, it is not ethical to recruit a large sample size and burden vulnerable older adults with participation. Besides, at this point of the study, it is not known how many independent variables will be included in the model and that depends on the results of the factorial analysis that precedes the logistic model. Therefore, I aim to treat the research about the associated factors with the presence of MCI (RQ4) as a pilot to gather preliminary data. This approach can help refine the research design and hypotheses, and the results can be used to justify the need for a larger study

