in the future. Additionally, based on the data, a simpler model with only the strongest predictors will be used to produce a more reliable regression model. Thus, for an initial study on a new test, correlational analysis is the most practical choice, allowing us to assess concurrent validity without requiring an excessively large sample size.

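### The 0.8 power printed in 3.3 describes neither a test of r = 0.7 against zero at 58 people nor the point-estimate rule by which 3.9 judges concurrent validity

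*Protocol*

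**What the plan says.** Section 3.3 of the protocol opens its justification with "The correlational analysis was selected for determining the sample size of this study" and gives as the reason that "the diagnostic accuracy and validity testing are the primary objectives of this project". It describes the study as "designed with a statistical power of 0.8, an alpha level of 0.05, and a medium effect size of 0.7" and arrives at a minimum of 58 participants, 29 with MCI and 29 with typical cognition. It does not say whether 0.7 is a correlation, a standardised mean difference or something else, whether alpha is one- or two-sided, or what null value applies. The section closes by tying the choice to concurrent validity: "correlational analysis is the most practical choice, allowing us to assess concurrent validity without requiring an excessively large sample size".

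Section 3.9 analyses RQ2 by correlating the game metrics with the total and sub-scores of the MoCA and Qmci. Its verdict is that if r is "positive closer to one, it means that the concurrent validity of G3 as an MCI screening tool is good". Nothing else qualifies it. The other research questions are handled differently in the same section: RQ1 and RQ5 each have a named test at alpha 0.05, RQ3 has bands for the AUC, and RQ6 has score cut-offs for the SUS.

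**The concern.** Power and alpha are properties of a decision rule with a null value and a rejection region. The RQ2 verdict has neither: it turns on how near a point estimate lies to one. A study can reject zero with an r far from one, so power for the first says nothing about the second.

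This matters because RQ2 is the analysis the sample size is said to rest on, and concurrent validity is one of the two primary objectives. A reader who sees 0.8 and 0.05 in 3.3 will take the validity conclusion to have those error rates. As written it has none that can be stated, and what counts as close enough to one can be settled after r is known. The imprecision of r at this sample size is also left out of the verdict.

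**Working it through.** **Inputs.** From 3.3: n = 58 (29 + 29), power 0.8, alpha 0.05, effect size 0.7. From 3.9: the RQ2 verdict, which has no cut-off. Assumptions made here: 0.7 is a Pearson correlation, alpha is two-sided, and the two variables are continuous and roughly bivariate normal.

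**1. Can 58 be reproduced?** For one correlation against zero, n = ((z_alpha + z_power)/atanh(r))² + 3. With atanh(0.7) = 0.867:

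- two-sided: ((1.960 + 0.842)/0.867)² + 3 = 13.4, so 14 people
- one-sided: 12 people

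Neither gives 58. In reverse, 58 people give 80% two-sided power at r of about 0.36. Other readings of 0.7:

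| Reading | Total n |
|---|---|
| Two-group standardised difference 0.7, two-sided | 66 (68 with the t distribution) |
| The same, one-sided | 52 |
| The same with 10% dropout added | 52/0.9 = 58 |
| Difference 0.7 converted to r = 0.33, two-sided / one-sided | 70 / 56 |
| Two independent correlations, q = 0.7, one-sided | 28.2 per group, so 29 + 29 = 58 |

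The readings that reach or approach 58 need inputs the protocol does not state, and none of them is the RQ2 verdict.

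**2. Test against zero at n = 58.**

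- Critical |r| = t/√(t² + 56), with t the 97.5% point on 56 degrees of freedom: 0.259. An observed r of 0.26 has a 95% interval of about 0.00 to 0.49.
- Power at r = 0.7: Φ(0.867 × √55 − 1.960), which is above 0.999.

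**3. The written verdict at n = 58.** Since 3.9 gives no cut-off c, the chance that the observed r reaches c when the true r is 0.7 can only be shown over a range (simulation):

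| Assumed c | 0.5 | 0.6 | 0.7 | 0.8 | 0.9 |
|---|---|---|---|---|---|
| P(observed r ≥ c) | 0.99 | 0.91 | 0.52 | 0.05 | 0.00 |

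By the Fisher approximation it equals 0.80 only at c of about 0.64, a value that appears nowhere in the protocol.

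**4. What 58 people do deliver.** The 95% interval is tanh(atanh(r) ± 1.96/√(n − 3)).

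- Pooled, n = 58, r = 0.70: 0.54 to 0.81, a half-width of (0.81 − 0.54)/2, about 0.14.
- One group, n = 29, r = 0.70: 0.45 to 0.85.

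For a rule that the lower limit must exceed 0.4 (illustrative only, atanh = 0.424), power at true r = 0.7 is Φ((0.867 − 0.424)√(n − 3) − 1.96):

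- n = 58: 0.91 by the formula, 0.92 by simulation
- n = 29: 0.62 by the formula, 0.64 by simulation, so about 65%

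With a minimum of 0.5 instead, pooled power is 0.67 by simulation.

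**The case against.** The strongest reply is that 3.9 offers interpretive guidance, not a pass/fail rule. It sets out to explore an association, and its wording is a gradient, like its remark that a ROC curve nearer the upper left corner means higher accuracy. RQ2 in section 1.3 asks whether there is any relationship. Power for a correlation test suits that question, and the sentence on closeness to one could be a second step that describes strength. Intervals, p-values and a minimum acceptable r may also sit in a statistical analysis plan that is not shown.

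Part of this stands. The two-step reading softens the mismatch, and the absence of detail is not itself the point. But the sentence in 3.9 states a conclusion about validity, worded like the RQ1 and RQ5 verdicts. The two-step reading does not rescue the 0.8 either: a test against zero at r = 0.7 and 58 people has power above 0.99.

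Four stronger inferences should be resisted:

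- **That the true chance of success is 52%, not 80%.** That figure needs a cut-off of 0.7, which the protocol never sets. The same calculation gives 0.99 to 0.00 over other cut-offs.
- **That the power figure misdescribes the rule for the whole primary objective.** Section 3.3 names two objectives. The RQ2 sentence bears only on concurrent validity; diagnostic accuracy is judged under RQ3.
- **That 0.4 is the right minimum, or that 92% is the study's power.** The 0.4 has no source in the documents. The 92% holds for one pooled, continuous metric-test pair, whereas RQ2 covers six metrics, two of them binary, against totals and sub-scores, and is posed for both cognitive groups.
- **That 58 people are too few.** Nothing here shows that, and the protocol already presents itself as a feasibility study with a limited sample.

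**Conclusion.** The point holds in limited form. The power statement in 3.3 and the RQ2 verdict in 3.9 do not belong to the same criterion, and this affects one of the two primary objectives. That the two criteria differ does not depend on how 0.7 is read: power and alpha describe a hypothesis test, and closeness of a point estimate to one is not a test.

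The size rests on taking 0.7 as a correlation tested two-sided against zero. Then 80% power needs about 14 people, significance at 58 starts at |r| of about 0.26, and power at 0.7 exceeds 0.99. On other readings 58 can be approached or reached, but only with inputs that are not stated, and the 0.8 still does not attach to the written verdict. The correction is worth making before r is seen. It questions what is claimed for the sample size, not the number recruited.

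**What to change.** **In 3.9, RQ2.** Replace the point-r sentence. Report each correlation with its 95% confidence interval (Fisher z or bootstrap). Name one main metric-test pair and say whether it is analysed pooled or within group. State that concurrent validity is supported when the lower limit, taken in the direction expected for that metric, exceeds a minimum that the sponsor sets and justifies in advance. Direction needs saying because, for number of errors and playing time, a higher value means worse performance and the expected r with a cognitive score is negative.

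**In 3.3.** State the metric of the 0.7. Replace the 0.8 with the figure that 58 people deliver for the new rule, or with the expected precision: a 95% interval of 0.54 to 0.81 at a pooled r of 0.70. With an illustrative minimum of 0.4, the entry would read about 92% power pooled and about 65% within one group of 29, for a true r of 0.70.

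**Cost.** A few sentences in 3.9 and one figure in 3.3, with no added participants or data. The downside is that a moderate point r with a wide interval can no longer be called good. With a 0.4 minimum, an observed pooled r below about 0.60 would fall short, since tanh(0.424 + 1.96/√55) = 0.597.

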Finally, the ROC curve will be calculated and plotted. TPR and FPR need to be calculated for various threshold values. Then, TPR (y-axis) against FPR (x-axis) for each threshold will be plotted. The closer the ROC curve is to the upper left corner, the higher the test's accuracy, as this position represents a sensitivity of 1 and a false positive rate of 0 (specificity of 1). An ideal ROC curve has an AUC of 1.0. An AUC of 0.5 indicates no discrimination, 0.7 to 0.8 is acceptable, 0.8 to 0.9 is excellent, and above 0.9 is considered outstanding (155,156).

To investigate if the game performance is an associated factor with cognitive status controlled by demographic variables (RQ4), logistic regression analysis (157) will be used. For all variables, categories will be combined into broader categories, when possible, to improve the power of the logistic regression model (158). Chi-Square test will be used to determine if there is a significant

association between variables and cognitive status. Principal Component Analysis (PCA) will be used to reduce the number of variables in a dataset while preserving as much variability (information) as possible (159). To determines which factors to retain based on explained variance, and Eigenvalue Cut-Off of 1 will be applied. Following this, logistic regression model will be run with the included variables. The performance of the logistic regression model with be evaluated using ROC analysis and test characteristics (160).

To compare the differences between the level of anxiety while playing the game and while traditional cognitive tests in older adults with typical cognition and with MCI (RQ5), either the Paired t-test or Wilcoxon Signed-Ranks test (155) will be used as appropriate, with an α level of 0.05, to compare the anxiety level in the two conditions- while playing the games and while performing MoCA. If the mean difference is significant and lower while playing the game compared with MoCA and Qmci, it means that the G3 causes less anxiety compared to the traditional cognitive screening tools.

To explore the usability of the game-based screening (RQ6), the SUS results will be calculated and interpreted as follows:

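### RQ3 fixes neither an index score nor a cut-off for the game, so sensitivity and specificity would be reported from a cut-off found in the same 58 people and would be too favourable

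*Protocol*

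**What the plan says.** All places are in the Protocol.

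- **Section 3.3, Sample size.** It states that "diagnostic accuracy and validity testing are the primary objectives of this project". The sizing statement reads "a statistical power of 0.8, an alpha level of 0.05, and a medium effect size of 0.7, requires a minimum sample size of 58 participants"; recruitment is to be "Twenty-nine older adults (65 and above) who meet the diagnostic criteria for MCI, and 29 older adults with typical cognition".
- **Section 3.6, Variables.** The index measure is "Game performance collected through various game metrics". Six are listed. Four are numerical: total time, errors, list checks and game accuracy. Two are binary: budget management and completion ("The ability to complete the game: This binary variable"). No metric is marked as the lead and no composite is defined. Game accuracy has a 0 to 100 range and a direction, but no scoring formula.
- **Section 3.9, Data analysis, RQ3.** The wording is "To investigate the diagnostic accuracy of the game-based screening (RQ3), formulas will be used as follows", followed by the true/false positive/negative formulas. For the ROC curve, "TPR and FPR need to be calculated for various threshold values". No cut-off is given and no rule for choosing one. The AUC is then read against bands: "0.7 to 0.8 is acceptable, 0.8 to 0.9 is excellent".
- **Section 3.1, Study design.** The game has no earlier use as a cognitive screen, so the document supplies no cut-off from previous work.
- **Section 3.11, Limitations.** Small sample size and misclassification are acknowledged. Optimism from choosing a cut-off or metric in the same data is not.

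**The concern.** A two-by-two accuracy table needs one score and one definition of a positive result. RQ3 has the formulas but not the inputs. Two distinct biases can follow, and they should be kept apart.

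1. **Choice of cut-off.** A cut-off picked because it separates these 58 people well fits their noise as well as the signal. Sensitivity, specificity and accuracy at that cut-off are too high. The AUC is unaffected. This bias arises even with a single metric.
2. **Choice of metric.** If several metrics are examined and the best-looking one is presented as the result, both its AUC and its sensitivity and specificity are too high. This depends on a selection that the protocol leaves open but does not announce.

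At stake is the main message of the study: accuracy figures that would not hold in new people, and an AUC that could be placed in a better band than the game deserves.

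**Working it through.** **Plan's own figure.** The 58 reproduces as a one-sided comparison of two independent correlations with Fisher-z difference q = 0.7: n per group = 2 × ((1.645 + 0.842)/0.7)² + 3 = 28.23, so 29 per group and 58 in total. Section 3.3 states neither the sidedness nor the effect-size type, so this is a reconstruction. It shows that the size was not set for AUC, sensitivity or specificity. For scale, at 29 v 29 the Hanley-McNeil standard error of an AUC of 0.70 is 0.069, and an observed sensitivity of 23/29 has an exact 95% interval of 0.60 to 0.92.

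**Inputs.** From the protocol: 29 per group; six metrics, four numerical and two binary; AUC bands starting at 0.70 and 0.80. Assumed, because the protocol gives none: true AUCs, correlation between metrics of 0.3 to 0.7, normal scores with equal variance, and direction of each metric fixed in advance.

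**Best attainable value.** With group separation d = √2 × Φ⁻¹(AUC), the largest true value of J = sensitivity + specificity - 1 is 2Φ(d/2) - 1.
- AUC 0.65: d = 0.545, Φ(0.2725) = 0.6074, J = 2 × 0.6074 - 1 = 0.21.
- AUC 0.75: d = 0.954, Φ(0.477) = 0.683, J = 2 × 0.683 - 1 = 0.37.

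**Bias 1: one metric, cut-off maximising J in the same data** (simulated studies, 29 v 29):

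| True AUC | Best attainable J | Mean reported J | Excess per measure |
|---|---|---|---|
| 0.65 | 0.21 | 0.32 | (0.32 - 0.21)/2 ≈ 0.05 |
| 0.75 | 0.37 | 0.46 | (0.46 - 0.37)/2 ≈ 0.05 |

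The mean AUC of that single metric is unbiased. The excess is the average over sensitivity and specificity.

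**Bias 2: the metric with the highest AUC is also selected.** Chance that the reported AUC reaches 0.70 when the best true AUC is 0.65:

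| Scenario | One pre-named metric | Best of six |
|---|---|---|
| Six equally accurate, all continuous, correlation 0.3 to 0.5 | about 25% | 60 to 71% |
| Equally accurate but two dichotomised, as in section 3.6, correlation 0.3 to 0.7 | about 25% | 47 to 64% |
| Unequal (0.65, 0.60, 0.60, 0.55, 0.55, 0.55; two dichotomised), correlation 0.3 to 0.7 | about 25% (the truly best metric) | 28 to 36% |

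Mean optimism in the selected AUC is about 0.05 to 0.08 with six equally accurate continuous metrics, and slightly less when two are dichotomised. With unequal metrics the selected AUC averages 0.66 to 0.68 against 0.65. With one dominant metric (0.75, the others 0.60 to 0.65) it averages 0.75 to 0.76 against 0.75, so the inflation almost vanishes.

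At the upper band, with true AUC 0.75 and equally accurate metrics of which two are dichotomised, the best of six reaches 0.80 in 42 to 57% of studies, against 21 to 25% for one named metric.

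**The case against.** **Selection of the best metric is not stated.** A reader might infer that section 3.9 commits to six ROC curves and headlines the highest. It does not. It speaks of one ROC curve, and if every metric were reported with its own AUC, none of those AUCs would be biased. This stands, so the metric-selection part is conditional.

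**Computing rates over thresholds is not an error.** Every ROC curve is built that way, and it does not inflate the AUC. This stands too. Moreover, each binary metric has only one possible cut-off.

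**The 60 to 71% figure is close to a worst case.** It needs six equally accurate continuous metrics, and the protocol gives no ground for assuming that. It is the upper end of a range.

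**Much of this is analysis-plan detail.** A cut-off rule, intervals and a bootstrap are commonly left to a statistical analysis plan, which is not at hand, so their absence alone would be no finding. What the test is and what counts as positive is different: it defines a primary objective. Section 3.9 goes down to formulas, plotting steps and interpretation bands without supplying it.

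**This is a first feasibility study.** No earlier cut-off exists, the protocol concedes that the sample should be larger, and the AUC bands trigger no decision. Exploring thresholds is therefore legitimate. But a cut-off found in these data is exactly the case in which uncorrected sensitivity and specificity are too high.

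**The RQ4 logistic model does not fill the gap.** It answers a different question, section 3.3 treats it as a pilot, and its ROC evaluation mentions no validation either.

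**Conclusion.** The point holds in a limited form. RQ3 serves a primary objective but leaves its index score and cut-off open among six metrics. Because the game has no screening history, the cut-off would almost certainly come from the same 58 people.

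The firm part is the cut-off: roughly 5 points too high on each of sensitivity and specificity, at true AUC 0.65 or 0.75, if a cut-off maximising their sum is chosen in-sample. This needs no assumption about how many metrics are tried.

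The conditional part is the AUC. If the best-looking metric is also headlined, the optimism runs from almost none to about 0.08. The chance of reaching 0.70 at a best true AUC of 0.65 then rises from about 25% to somewhere between about 30% (unequal metrics) and 70% (equal, all continuous). All these sizes rest on assumed true AUCs, correlations and normal scores. The protocol does not support the stronger statement that the plan will report the best of six.

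**What to change.** Before data collection, amend sections 3.6 and 3.9 as follows.

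- Name one numerical index score for RQ3, either one metric or a fixed composite, with its scoring formula and the direction that indicates MCI. If game accuracy is chosen, its formula must be written down, since section 3.6 gives only the range and direction.
- Label the other metrics secondary.
- State the cut-off, or the rule by which it will be chosen.
- Report sensitivity, specificity and accuracy corrected for optimism by bootstrap (repeating the cut-off choice in each resample) or by cross-validation, with 95% intervals.
- Apply the AUC bands to the index score's AUC, shown with its interval. This AUC needs optimism correction only if a metric is selected or a model is fitted in the data.

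The cost is protocol wording and a short bootstrap, with no extra participants or visits. The downside is slightly less favourable headline figures.
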